#### 1.3. Potential Benefits and Risks

#### **1.3.1.** Potential Benefits

As described in Section 1.2.4, preliminary data from the Phase 1b/2 VT3996-201 study indicate that at the RP2D, the combination of nanatinostat and valganciclovir was generally well-tolerated and demonstrated clinical activity in a population of heavily pretreated patients with a variety of recurrent EBV+ lymphomas, the majority of whom were refractory to their last therapy prior to entering the study. Patients with relapsed/refractory DLBCL and ENKTL showed the most promising response rates, including CRs in 2 patients with primary refractory DLBCL. The combination appears to be highly active in patients with recurrent PTCL and ENKTL, including those who had failed stem cell transplantation. The oral administration of both

nanatinostat and valganciclovir is an added benefit to patients, as they can take their study treatment at home. The eligibility of adolescents (≥12 years of age) with PTLD in this study is supported by the guidance in which the histology and biologic behavior of the cancer under study is the same as adult patients, or when the molecular target of the investigational treatment is relevant to both adult and adolescent patients (*federalregister.gov/d/2019-04582*).

#### 1.3.2. Potential Risks

HDAC inhibitors are potent inducers of the EBV lytic cycle; the production of infectious virus by virtue of HDACi-mediated induction of the tumor lytic cycle is a clinically documented AE described in a monotherapy clinical trial with the HDACi romidepsin, but this potential safety issue can be abrogated by the coadministration of ganciclovir (GCV). In the Phase 1b/2 VT3996-201 study, patients' EBV genome levels have been serially monitored. There have been no reported cases of EBV or CMV reactivation, and no significant elevations of plasma EBV DNA have been noted thus far in these patients receiving nanatinostat co-administered with valganciclovir, indicating that this combination is potentially preventing EBV viremia.

EBV reactivation has been reported in 3 ENKTL patients receiving romidepsin as a monotherapy (Kim 2016). Romidepsin-induced EBV reactivation was also reported in 2 patients with relapsed PTCL who were receiving romidepsin in a Phase 2 trial (Ritchie 2009). The romidepsin prescribing information describes a risk of reactivation of DNA viruses, including EBV (ISTODAX® USPI 2021 (Celgene 2021)). Due to the reported activity of HDACi's in PTCL, the potential anti-tumor activity of nanatinostat as a monotherapy will be evaluated in 10 patients with PTCL in this study. Because of the risk of EBV reactivation in patients with EBV+ lymphomas receiving monotherapy with HDACi's, these patients will be monitored closely for clinical signs and lab evidence of EBV or other viral reactivation during their short course (6 weeks) of monotherapy.

Dosing for valganciclovir is consistent with the approved dose. Any necessary dose adjustments (eg, in the case of creatinine elevations) will be made according to the prescribing information. The safety profile for this dose of valganciclovir is well defined and appears acceptable as part of a treatment regimen for patients with relapsed/refractory lymphoma. Further information about valganciclovir can be found in the prescribing information (VALCYTE® USPI 2021 and SmPC 2018 (Genentech 2021, Roche 2018).

Pertaining to the coadministration of nanatinostat and valganciclovir, both drugs exhibit overlapping toxicities (ie, thrombocytopenia and renal dysfunction) that may be increased in frequency or severity in combination.

In addition, in prior clinical studies other toxicities reported for one or both agents include fatigue, atrial fibrillation, nausea/vomiting, anemia, leukopenia, and neutropenia.

As QTc prolongation has been reported with other HDAC inhibitors, (Gryder 2012), medications with a known risk of prolonging the QT interval should be avoided (Section 5.5.4).

As with any new combination, toxicities which have not been seen with either agent alone or with combinations of similar agents may become manifest.

Available clinical data indicates a 2- to 2.5-fold higher systemic exposure of nanatinostat with the co-administration of valganciclovir, which is expected, as valganciclovir/ganciclovir is the MDR1 and BCRP inhibitor, and nanatinostat is the substate of MDR1 and BCRP transporters.

The systemic exposure of ganciclovir from nanatinostat and valganciclovir co-administration is consistent with that from valganciclovir monotherapy reported in the literature.

Further information about the safety profile of nanatinostat as a single agent and in combination with valganciclovir can be found in the current IB.

## 1.3.3. Risks Related to Study Procedures

Potential study-related risks include (but are not limited to) collection of new tumor samples, blood draws, radiological assessments, and concomitant medications in case of AEs. More information can be found in the consent form.

# 1.3.4. Risk Management Strategies

The risks to patients in this study will be minimized by compliance with the eligibility criteria (eg, use of an eligibility checklist to approve enrollment) and study procedures, attentive medical monitoring, use of concomitant medications appropriate for the situation (eg, to manage AEs), and following guidance for dose adjustments (outlined in Section 5.4). Patients receiving nanatinostat monotherapy will be closely monitored for potential EBV reactivation and will have a disease response assessment 2 weeks earlier than patients in the combination arm.

The benefit-risk balance of the oral treatment regimen with nanatinostat and valganciclovir is anticipated to be positive for the target study population of relapsed/refractory EBV+ lymphoma patients who have previously received 1 or more prior therapies and in the opinion of the Investigator have exhausted all standard therapies.

#### 2. OBJECTIVES AND ENDPOINTS

The study objectives and related endpoints are presented in Table 2. Details of the statistical analysis are described in Section 9.

**Table 2:** Objectives and Endpoints

Objective(s)	Endpoint(s)					
Primary	Refer to Section 9.6.1 for methods of analysis.					
To evaluate the anti-tumor activity of the combination treatment of nanatinostat (Nstat) with valganciclovir (VGCV) based on objective tumor response rates	Objective response rate (ORR) as assessed by an Independent Review Committee (IRC) – defined as the proportion of patients who achieve a complete response (CR) or partial response (PR) using the 2007 International Working Group (IWG) criteria (Cheson 2007); Table 13. The Investigator will also use the 2007 IWG criteria for assessment of progression/relapse and for any clinical decisions requiring assessment of disease progression/relapse.					
Secondary	Refer to Section 9.6.2 for methods of analysis.					
To determine the duration of tumor control	Duration of response (DOR) – defined as the interval from the date of first observed CR or PR to the date of disease progression, death due to any cause, or last adequate (radiographic) response assessment.					
	• Time to next anti-lymphoma treatment (TTNLT) – defined as the interval from the start of study drug treatment to date of next anti-lymphoma treatment.					

Objective(s)	Endpoint(s)
	Progression-free survival (PFS) – defined as the interval from the start of study drug treatment to the date of first documented disease progression or death from any cause, whichever occurs first.
	• Time to progression (TTP) – defined as the interval from the start of study drug treatment to date of disease progression.
To determine survival outcomes	Overall survival (OS) – defined as the interval from the start of study drug treatment to date of death, for any reason.
To describe the safety profile of the combination treatment of Nstat with VGCV	Incidence and severity of treatment-emergent adverse events (TEAEs).     Adverse events will be graded according to National Cancer Institute (NCI)     Common Terminology Criteria for Adverse Events (CTCAE), version 5.0.
To generate pharmacokinetic (PK) data with the intended commercial dose and administration of Nstat	Pharmacokinetic (PK) parameters (eg, time to maximum plasma concentration [t max ], maximum plasma concentration [C max ], area under the plasma concentration-time curve [AUC]).
Exploratory	Refer to Section 9.6.3 for methods of analysis.
Explore correlation of baseline PD-L1 expression and other immune checkpoint molecules with outcome	
 
Expression of PD-L1 and other immune checkpoint molecules in tumor
 
Tumor-infiltrating lymphocyte (TIL) counts (eg, CD3, CD4, CD8)
 
EBV-associated genes/proteins (eg, EBER, BZLF-1/ZTA, LMP-1, BGLF-4/PK, BXLF-1/TK, BRLF-1Rta)
 

Evaluate potential biomarkers of activity of combination therapy	
 
Histone H3 acetylation
 
Plasma EBV DNA levels
 
RNA expression of selected immunological genes
 
Flow cytometry/IF/IHC for immune cell markers
 

Identify potential resistance markers to therapy	EBER, LMP-1, TIL counts, PD-L1 and other immune checkpoint molecules; markers related to resistance

## 3. STUDY DESIGN

The purpose of this study is to determine the efficacy of the combination treatment of nanatinostat with valganciclovir in patients with relapsed/refractory EBV+ lymphomas. No therapies are currently established for the treatment of EBV+ lymphoma; with use of standard therapies for the lymphoma subtypes, outcomes such as PFS and OS are increasingly recognized to be inferior for EBV+ lymphomas such as EBV+ DLBCL (NOS), HL, and PTCL, creating an unmet need for these patients. Promising preliminary safety and efficacy of the combination of oral nanatinostat and oral valganciclovir has been demonstrated in the VT3996-201 Phase 1b/2 study in heavily previously treated (median of 2 prior therapies) patients with a variety of relapsed/refractory EBV+ lymphomas, 75% of whom were refractory to their most recent therapy prior to enrolling in the study (Porcu 2020, Haverkos 2021).

Since there are no clinical monotherapy data with nanatinostat in lymphoma patients, and other HDAC inhibitors have demonstrated activity in patients with PTCL, nanatinostat will also be evaluated as monotherapy in patients with PTCL. The first 20 PTCL patients enrolled into the study will be randomized to receive nanatinostat monotherapy (n = 10) or nanatinostat plus valganciclovir combination therapy (n = 10). Patients receiving nanatinostat monotherapy may have the option to cross over to combination therapy (see Section 3.1).

An Independent Review Committee (IRC) will be established to determine the ORR. A Study Steering Committee (SSC) composed of study Investigators will be established to i) manage the overall stewardship of the study according to the protocol, and ii) to recommend and approve any modifications needed.

# 3.1. Description of Study Design

This is an open-label, multicenter, multinational single-arm, Phase 2 basket design study, utilizing Simon's 2-stage design options for discontinuing enrollment into each cohort where treatment appears to be futile (Simon 1989). The study will include 7 cohorts of patients with the following EBV+ relapsed/refractory lymphomas:

- Cohort 1: EBV+ DLBCL, NOS
- Cohort 2: ENKTL
- Cohort 3: PTCL, including PTCL-NOS and AITL
  - Cohort 3a: Nanatinostat monotherapy
  - Cohort 3b: Nanatinostat + valganciclovir
- Cohort 4: HL
- Cohort 5: PTLD
- Cohort 6: Lymphomas associated with HIV infection (HIV-L): Plasmablastic, Burkitt, Hodgkin, and DLBCL
- Cohort 7: EBV+ lymphomas other than Cohorts 1, 3, 4, 5, and 6 above (Cohort 7 will not enroll patients in France)

In Stage 1, 6 cohorts (Cohorts 1, 2, 3b, 4, 5, and 6) will enroll up to 10 patients each. Any cohort that fails to enroll any patients within 1 year from the date the first patient is enrolled in the study will be considered for termination of enrollment. Enrollment in Cohorts 2, 4, and 6 has been closed as of 17 October 2023, 24 August 2023, and 24 August 2023, respectively. Patients currently enrolled in these cohorts may continue to receive study treatment per protocol until which time treatment discontinuation is required as defined in Section 7.2.3.

All cohorts that have a response in 2 or more patients in Stage 1 will continue to enroll patients in Stage 2, for a total of 21 patients in each cohort (Figure 2). If  $\geq$ 7 responses are observed in the initial 21 patients in any cohort, then enrollment will be expanded to include up to 120 additional patients in that cohort (N=141), with the possibility of performing an interim efficacy analysis in that cohort to be described in the statistical analysis plan. Cohort 3a will not enroll beyond the initial 10 patients, regardless of the number of responders in Stage 1.

To evaluate the activity of single-agent nanatinostat, the first 20 patients enrolled with PTCL will be randomized 1:1 to either nanatinostat monotherapy (20 mg PO once daily on Days 1 to 4 per week in Cohort 3a) or nanatinostat plus valganciclovir (in Cohort 3b). Following a disease response assessment at 6 weeks, patients in Cohort 3a with a CR or PR will continue nanatinostat monotherapy. Those in Cohort 3a with stable disease at 6 weeks or disease progression at any time (confirmed by CT or MRI) will have the option to cross over to combination therapy for the remainder of the study. Patients must complete the End of Monotherapy Disease assessment and

qualify (labs, no sign of CNS disease progression and Eastern Cooperative Oncology Group [ECOG]) prior to beginning Cycle 1 Day 1 of the nanatinostat plus valganciclovir combination therapy.

Cohort 7 will be closed to enrollment when all other cohorts are closed, regardless of the number of patients recruited at that time and will not be subject to the decision criteria of the Simon's 2-stage design.

It is thus estimated that up to 486 patients in Cohorts 1 to 6 may be enrolled for combination therapy, of which approximately 60 would be enrolled in Stage 1, 66 would be enrolled in Stage 2, and up to 360 would be enrolled in the post-Stage 2 expansion cohorts. Additional patients (n=10) with PTCL will be enrolled in Cohort 3a for nanatinostat monotherapy, and patients with lymphoma subtypes other than those assigned to Cohorts 1, 3, 4, 5, and 6 may be enrolled into Cohort 7 (with the exception of France; see above).

If 10 patients of a given lymphoma subtype are enrolled into Cohort 7, then the Simon's decision criteria will be applied to determine whether or not to add patients in Stage 2 for that subtype. If none of the subtypes represented in Cohort 7 enrolls at least 10 patients, efficacy data collected on those patients will be listed, but not summarized by group. All patients will be summarized for safety, regardless of decision to discontinue enrollment into any cohort.

[figure not shown]
Patients enrolled in Cohorts 1 to 7 (with the exception of Cohort 3a), and patients crossed over from Cohort 3a will receive intermittent dosing of nanatinostat and continuous valganciclovir in 28-day cycles as follows:

- a. Nanatinostat 20 mg orally once daily on Days 1 to 4 per week (ie, 4 days on, 3 days off)
- b. Valganciclovir 900 mg orally once daily. Patients with a CrCl 50-59 mL/min at study entry will receive valganciclovir 450 mg orally once daily as per Table 4.

For adolescent patients, see Section 5.2.2 for appropriate dosing recommendations for valganciclovir. Patients who develop disease progression but, in the opinion of the Investigator, would still benefit from continuing study drug may continue treatment with nanatinostat and valganciclovir after agreement with the Sponsor, provided that they are i) asymptomatic from or have no overt signs of disease progression; and ii) have a performance status of 0-1. It is recommended to perform an interval follow-up radiologic disease assessment before the next scheduled time point. Such patients will be recorded as having had a PFS event.

All patients will be monitored at weekly intervals through the first cycle of treatment, and then at 2-week intervals thereafter. Tumor response will be evaluated after every 2 cycles  $\times$  3, and after every 3 cycles thereafter. The responses will be assessed by both the Investigator and an IRC.

Figure 2: Study Design

Note: Patients enrolled with PTCL will be randomized 1:1 to either nanatinostat monotherapy (in Cohort 3a) or nanatinostat plus valganciclovir (in Cohort 3b).

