## 1.2.4. Clinical Experience with Nanatinostat Plus Valganciclovir in EBV+ Lymphoma

A single arm Phase 1b/2 dose escalation/expansion study of nanatinostat in combination with valganciclovir (Study VT3996-201) is being conducted in patients with relapsed/refractory EBV+ lymphoma. Key eligibility criteria for enrollment included age  $\geq$ 18 with histologically confirmed EBV+ lymphomas,  $\geq$ 1 prior lines of therapy and no curative treatment options per investigator. In Phase 1b (n=25), the RP2D of nanatinostat (20 mg daily, Days 1 to 4 per week) and valganciclovir (900 mg daily) was selected based on evaluation of the following dose levels:

• Cohort 1 (n = 7): nanatinostat 10 mg oral twice daily + valganciclovir 900 mg oral twice daily (20+1800)

- Cohort 2a (n = 5): nanatinostat 5 mg oral twice daily + valganciclovir 450 mg oral twice daily (10+900)
- Cohort 2b (n = 4): nanatinostat 10 mg oral once daily + valganciclovir 450 mg oral once daily (10+900)
- Cohort 2c (n = 4): nanatinostat 10 mg oral once daily + valganciclovir 900 mg oral once daily (10+900)
- Cohort 3 (n = 5): nanatinostat 20 mg oral once daily, Days 1 to 4/week + valganciclovir 900 mg oral once daily (20+900)

In Cohort 1, 3 of the first 4 patients enrolled developed DLTs (Grade 4 neutropenia × 29 days, Grade 3 thrombocytopenia × 6 days, Grade 4 thrombocytopenia × 8 days), and 3/4 patients developed Grade 1 and 2 creatinine elevations. The picture of cytopenias and creatinine elevations prompted a 50% dose reduction in valganciclovir to 450 mg twice daily; 3 more patients were subsequently enrolled into the cohort. Following this, 1 patient developed a DLT (uncomplicated Grade 3 thrombocytopenia × 7 days), therefore, Cohort 1 was considered to have exceeded the MTD. In Cohort 2, across the 3 cohorts (2a, 2b, 2c; n = 13), there were no DLTs reported. The Safety Review Committee (SRC) made the recommendation to proceed in Cohort 3 with nanatinostat 20 mg daily using an intermittent schedule for administration (ie, 4 days on, 3 days off) with valganciclovir 900 mg once daily. The dosing regimen for Cohort 3 was subsequently declared to be the RP2D, as no DLTs were reported.

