## 7.2.1. Treatment Cycles

For Cohorts 1, 2, 3b, 4, 5, 6, and 7, patients will receive nanatinostat/valganciclovir (nanatinostat 20 mg orally once daily on Days 1 to 4 per week and valganciclovir 900 mg orally once daily) continuously for 28-day treatment cycles. During treatment Cycle 1, visits will occur on Days 1, 8, 15, and 22. Starting at Cycle 2, visits will occur on Days 1 and 15. Each scheduled clinic visit has an allowable ±3-day window. Visit windows are not applicable to dosing. Should a visit occur during the ± 3-day window, patients will be instructed to continue following the 4 days on, 3 days off dosing cycle for nanatinostat.

For Cohort 3a, the PTCL patients randomized to monotherapy will begin with 6 weeks of nanatinostat monotherapy (20 mg orally once daily on Days 1 to 4 per week) with visits on Days 1, 15, 29, and 43. Each scheduled clinic visit has an allowable ±3-day window. If a patient has stable or progressive disease at the Day 43 visit, the patient will be offered the option to switch to nanatinostat/valganciclovir combination and follow the 28-day treatment cycles as described above. Patients must complete the End of Monotherapy Disease assessment and qualify (labs, no sign of CNS disease progression, ECOG) prior to beginning Cycle 1 Day 1 of the nanatinostat/valganciclovir combination therapy. If a patient has a response (complete or partial response) to nanatinostat monotherapy at the Day 43 visit, the patient will continue monotherapy treatment.

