Summary results will include the count and percentage of patients within each shift category and cohort.

Where applicable, hematology and chemistry results for selected parameters will be assigned a toxicity grade based on the U.S. Department of Health and Human Services *Common Terminology Criteria for Adverse Events (CTCAE)*, version 5.0 (27 Nov 2017). If criteria for a grade includes a quantitative component and a clinical intervention component, the clinical intervention component will be ignored where it cannot be programmatically addressed using available data and only the quantitative portion of the criteria will be considered. If the quantitative criteria for grading are equivalent for two grades and the differentiation is described by clinical interventions, the clinical intervention component will not be considered and the highest CTCAE grade will be assigned. Similarly, death related to AE (i.e., Grade 5) cannot be determined with available laboratory-based data collection and, thus, will not be

summarized as a category. Laboratory parameters that include multiple sets of criteria for each direction (e.g., separate criteria for potassium measures to assess hyperkalemia and hypokalemia) will be summarized separately to reflect each set of criteria.

Five-by-five contingency tables will be presented for laboratory tests where toxicity grading can be applied, to summarize the shift from the baseline grade to the worst post-baseline grade. Grades will be presented as none (Grade 0; i.e., measurements did not meet any CTCAE criteria for Grades 1 through 4), mild (Grade 1), moderate (Grade 2), severe (Grade 3), or life-threatening (Grade 4). Summary results will include the count and percentage of patients within each shift category.

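### The protocol states weekly Cycle 1 monitoring for all patients but schedules Cohort 3a every two weeks; the two rules need reconciling, and worst-value laboratory summaries for randomized Cohorts 3a and 3b are not like for like

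*Protocol*

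**What the plan says.** Protocol Section 3.1, repeated in the synopsis, sets one rule: "All patients will be monitored at weekly intervals through the first cycle of treatment, and then at 2-week intervals thereafter".

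Section 7.2.1 sets two. For the combination cohorts, including 3b: "During treatment Cycle 1, visits will occur on Days 1, 8, 15, and 22", and then "Starting at Cycle 2, visits will occur on Days 1 and 15". For Cohort 3a, six weeks of monotherapy "with visits on Days 1, 15, 29, and 43". The synopsis text on Cohort 3a and SAP Section 3.1 give the same four days. In Table 6, hematology, chemistry and adverse event review for 3a fall only on those days. Table 5 has hematology for the combination cohorts on Cycle 1 Days 1, 8, 15 and 22, then Cycle 2 Days 4 and 15. It thus labels the first Cycle 2 visit Day 4, where Section 7.2.1 says Day 1. For both schedules: "Each scheduled clinic visit has an allowable ±3-day window".

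SAP Section 4.6 keeps patients randomized to monotherapy, those who cross over and those randomized to the combination as separate groups for occurrence-based safety summaries. SAP Section 4.6.4 plans three-by-three tables of the shift to the worst post-baseline value, by cohort and through the end of the study, and five-by-five tables "to summarize the shift from the baseline grade to the worst post-baseline grade". SAP Section 4.1.2 lets unscheduled values count toward the worst value. SAP Section 4.1.1 plans no formal comparison of cohorts.

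**The concern.** There are two issues. First, a site treating a Cohort 3a patient cannot satisfy both monitoring rules. Without Day 8 and Day 22 visits the patient departs from Section 3.1 but complies with Table 6, so it is unclear what counts as a deviation.

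Second, a worst-of-several-draws summary depends on how many draws there are. Two groups with identical toxicity will show different worst grades if one is sampled more often. Cohorts 3a and 3b contain the study's only randomized patients, and Protocol Section 1.3.2 warns that overlapping toxicities may increase on the combination. Readers may well use the two sets of results to judge what valganciclovir adds. Part of any difference would come from the draw schedule.

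**Working it through.** The documents state no detection rate, so there is no plan figure to reproduce. The inputs are the scheduled days plus assumptions about episodes.

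**Draw counts.** Cycle 2 Day 4 is study day 28 + 4 = 32, and Cycle 2 Day 15 is 28 + 15 = 43.
- 3b (Table 5): Days 8, 15, 22, 32, 43, which is 5 post-baseline draws.
- 3a (Table 6): Days 15, 29, 43, which is 3.

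**Episode lengths.** The documents give none for monotherapy. The nearest figures are dose-limiting toxicities in the first cohort of the earlier combination study (Protocol Section 1.2.4): "Grade 4 neutropenia × 29 days, Grade 3 thrombocytopenia × 6 days, Grade 4 thrombocytopenia × 8 days", plus one further 7-day Grade 3 thrombocytopenia. I use 6, 7, 8 and 29 days as illustrations. Onset uniform in time is an assumption.

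**Simple form.** With draws every L days and an episode of d days, P(detect) = min(1, d/L). In Cycle 1, L is 7 in 3b and 14 in 3a. For d up to 7 the ratio is (d/14)/(d/7) = 1/2. From d = 14 both are 100%.

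**Actual days.** Onset is uniform over Days 1 to 28 (a span of 27 days). An episode is detected if a draw falls within d days after onset.

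| Duration | 3b | 3a | 3a/3b |
|---|---|---|---|
| 6 days | (6+6+6+2)/27 = 20/27 = 74% | (6+5)/27 = 11/27 = 41% | 0.55 |
| 7 days | (7+7+7+3)/27 = 24/27 = 89% | (7+6)/27 = 13/27 = 48% | 0.54 |
| 8 days | (21+4)/27 = 25/27 = 93% | (8+7)/27 = 15/27 = 56% | 0.60 |
| 29 days | 100% | 100% | 1.00 |

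**Visit windows.** Each visit was shifted independently by up to 3 days, with onset on Days 2 to 29 and 3b drawn on Day 29. Simulated miss rates in 3a and 3b were 60.1% and 26.3% (6 days), 53.2% and 18.1% (7 days), and 45.8% and 12.1% (8 days). Detection is therefore 39.9% against 73.7%, 46.8% against 81.9%, and 54.2% against 87.9%, with ratios 0.54, 0.57 and 0.62. Without windows the same setting gives 0.50, 0.50 and 0.57.

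**Onset over the whole six weeks.** With windows, onset on Days 2 to 43 and the Day 32 draw, detection is 40.7% against 64.7%, 47.8% against 73.0%, and 54.9% against 80.2%. The ratios are 0.63, 0.65 and 0.68. The gap shrinks because the schedules are nearly the same after Cycle 1.

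**The case against.** **The conflict may be loose drafting.** Every place that describes Cohort 3a specifically gives the same four days. The sentence after the weekly rule, on response assessment every two cycles, does not fit 3a's scans at Weeks 6, 14 and 22 either. The paragraph may describe the combination regimen only. That is a fair reading, but the text says all patients and concerns safety monitoring. SAP Section 4.7 already reports a Stage 2 response rate for PTCL, so the randomized patients have presumably been enrolled (an inference). Reconciling the text would then change few or no visits.

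**No comparison is planned.** This stands. Reporting is descriptive, with 10 patients per group. The three-by-three tables run to the end of the study rather than Day 43, and the five-by-five text does not specify display by cohort. The issue is how the tables will be read, not an invalid test.

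**The sizes are illustrative.** This also stands. The durations come from a combination dose level judged to exceed the maximum tolerated dose, whereas the regimen used here had no dose-limiting toxicities. Unscheduled draws count and adverse events are recorded continuously, so symptomatic episodes can surface between visits. These routes do not fully compensate, because an asymptomatic cytopenia has to be sampled before it can be acted on or reported.

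**Stronger readings that the documents do not support.**
- A reader might infer that 3a misses cytopenias twice as often. It is detection that is roughly halved. On the simple form the miss ratio is (1 − d/14)/(1 − d/7): 1.08 at 1 day, 2 only at 14/3 = 4.7 days, 4.0 at 6 days, and unbounded from 7 to 13 days.
- A reader might infer that monotherapy will look safer. That is a possible direction, not a result.
- A reader might set the schedule against "Patients receiving nanatinostat monotherapy will be closely monitored for potential EBV reactivation" in Protocol Section 1.3.4. That promise concerns viral reactivation. By Day 43, 3a has three post-baseline EBV DNA tests (Days 15, 29, 43) and 3b has two (Days 15, 32). The 3a disease assessment also comes two weeks earlier.
- A reader might infer that safety actions are generally delayed. Several Table 3 triggers act without a waiting period, and monitoring becomes about twice weekly once a toxicity is found.

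**Conclusion.** The contradiction over Cohort 3a's first-cycle monitoring is established by the text and needs no assumption. So is the difference of five against three scheduled post-baseline draws by Day 43 under Tables 5 and 6.

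The analytical consequence holds in a limited form. In Cycle 1, scheduled draws in 3a have about half the chance that 3b's have of detecting an asymptomatic cytopenia of up to about 7 days. The percentages for 6 to 8 days rest on uniform onset, borrowed durations, nominal visit days and no unscheduled draws. The effect disappears for long episodes. Worst-post-baseline laboratory summaries for randomized 3a and 3b are therefore not like for like. Nothing here shows which regimen is safer, and no primary or formal analysis is affected.

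**What to change.** 1. Reconcile Protocol Section 3.1 and the matching synopsis sentence with Section 7.2.1, the synopsis text on Cohort 3a, Table 6 and SAP Section 3.1. The sponsor decides which schedule applies.
2. In SAP Section 4.6.4, add one worst-grade and shift summary for the 20 randomized PTCL patients, restricted to scheduled draws before crossover on Days 15 and 43. The 3a Day 29 and 3b Day 32 draws may be included only as an approximate match and labelled so. They are three days apart and fall on different days of the dosing week.
3. Footnote the all-draw laboratory tables to say that scheduled draw frequency differed between 3a and 3b in Cycle 1.

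The cost is a wording change, one descriptive table for at most 20 patients and a footnote. The downside is that the restricted table discards some 3b draws, so it should sit beside the all-draw tables rather than replace them.
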